6.4.2 Ventilator Settings

The device is designed for use with standard adult ventilator settings. An intermittent positive pressure ventilatory mode (i.e., not constant positive airway pressure [CPAP] or t-piece) is required to activate the device to deliver aerosol during the inspiration phase. A Heat-Moisture Exchanger (HME) may be used in the device circuit.

6.4.3 Device Supply

Prior to the first dose of VentaProst for each patient, one delivery device setup will be dispensed. The serial numbers for the controllers, flow sensor, and nebulizer will also be recorded in the dispensing log.

Used and unused devices will be inventoried and returned to the Sponsor or Sponsor's designee.

6.4.4 Device Replacement

Devices may be replaced at any time if there is a suspicion of malfunction, but must be replaced if:

- The investigator suspects that, due to device malfunction, less than 90% of the total dose of study medication is being delivered. Reduced doses must be estimated and recorded in the patient's medical record and on the appropriate page of the case report form (CRF).
- The investigator suspects the device is not performing optimally for any reason.

6.4.5 Device Malfunction or Failure

One device (Aerogen Pro-X controller, Aerogen Pharma Breath Controller, Flow Sensor, Solo nebulizer, CNTS syringe, and associated components) is expected to perform throughout the duration of study treatment. If the controllers, Flow Sensor, CNTS syringe, or the Solo nebulizer are not functioning optimally for any reason, instructions for trouble-shooting provided in the device instruction for use manual should be followed. If one or more devices need to be replaced, the reason should be documented in the patient's medical record, dispensing log, and eCRF. Additional devices are provided for this purpose. The unique serial numbers of the new components will be recorded in the patient's medical record, dispensing log, and eCRF.

For device malfunction or complaints, the Sponsor or the Sponsor's designee should be contacted within 48 hours. Failed devices will be inventoried and returned to the Sponsor or the Sponsor's designee.

6.5 Blinding

Since this is an open-label study, there will be no blinding of the study medication.

6.6 Prior and Concomitant Therapy

For patients who receive study medication, any medication (including over-the-counter [OTC] medications) or therapy administered to the patient during the course of the study (starting at Screening and 30 days prior) will be recorded on the Prior and Concomitant Therapy eCRF. The Investigator will record any AE on the AE eCRF for which a concomitant medication/therapy was administered.

6.6.1 Prohibited Concomitant Therapy

Not applicable.

6.7 Investigational Product (IP) Supplies and Accountability

Investigational product supplies will not be sent to the Investigator(s) until the following documentation has been received by the Sponsor:

- Written proof of approval of the protocol and its informed consent forms (ICFs) by the Institutional Review Board (IRB)/Independent Ethics Committee (IEC) for the institution where the study is to be conducted.
- An Investigator-signed and dated FDA Form 1572.
- A signed and dated curriculum vitae of the Principal Investigator including a copy of the Principal Investigator's current medical license (required in the US) or medical registration number on curriculum vitae.

- A signed and dated clinical trial agreement.

The Investigator and study staff will be responsible for the accountability of all IP supplies (dispensing, inventory, and record keeping) following Aerogen Pharma instructions and adhere to Good Clinical Practice (GCP) guidelines as well as local and/or regional requirements.

Under no circumstances will the Investigator allow the IP to be used other than as directed by this protocol. IP will not be administered to any individual who is not enrolled into the study.

An accurate and timely record of the receipt of all IP; dispensing of IP to the patient; collection of unused IP; and subsequent return of unused IP to Aerogen Pharma must be maintained. This includes, but may not be limited to: (a) documentation of receipt of IP, (b) IP dispensing log, (c) IP accountability log, (d) all shipping service receipts, and (e) documentation of returned IP to the Sponsor. All forms will be provided by Aerogen Pharma. Any comparable forms that the investigational site wishes to use must be approved by Aerogen Pharma.

The supplies and inventory records must be made available, upon request, for inspection by the designated representative of Aerogen Pharma, a representative of the FDA, or a representative of a non-US health authority. All used and unused IP, including empty containers, are to be returned to Aerogen Pharma at the conclusion of the study, unless provision is made by Aerogen Pharma for destruction of supplies and containers at the investigational site. Upon completion of IP accountability and reconciliation procedures by investigational site personnel and documentation procedures by Aerogen Pharma personnel, IP that is to be returned to Aerogen Pharma, if necessary, must be boxed, sealed and shipped back to Aerogen Pharma following all local regulatory requirements.

A Clinical Research Associate (CRA) will review IP accountability during investigational site visits and at the completion of the study.

7. PHARMACODYNAMIC ASSESSMENTS

7.1 Primary Endpoint

Determination of the equivalent dose of VentaProst necessary to achieve a hemodynamic response that is not less than 90% of the effect observed with 50 ng/kg/min aerosolized Veletri.

7.2 Secondary Endpoints

The secondary endpoints that will be assessed include:

- Safety of VentaProst dosing regimen
 - Monitoring of adverse events (AEs), physical examinations, laboratory tests, and electrocardiograms
- Effect of VentaProst dosing regimen on:
 - Cardiovascular Parameters
 - Pulmonary Vascular Resistance (PVR)

- Pulmonary Arterial Pressure (PAP)
- Systemic Arterial Pressure
- Central Venous Pressure (CVP)
- Pulmonary Capillary Wedge Pressure (PCWP)
- Cardiac Output (CO)
- Oxygenation
 - Arterial Oxygen Saturation (SaO_2) or Oxygen Saturation by Pulse Oximetry (SpO_2)
 - Partial Pressure of Oxygen in Arterial Blood (PaO_2)
- Ventilator Support
 - FiO_2
 - Ventilator pressures
 - Ventilator volumes
 - Duration of intubation
- Number and type of cardiovascular medications required through end of study

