Medication History	X				
Physical Examination	X				X
Vital Signs/Weight/Height	X				X ¹²
12-Lead ECG	X				X
Spirometry	X ¹¹				
Clinical Laboratory Sampling	X				X
Serum Pregnancy Test	X				X
Inclusion/Exclusion Criteria	X	X			
Cardiac Surgery with CPB		X			
Administer Aerosolized Veletri			X ⁶		
Administer VentaProst				X ⁹	
Hemodynamic Parameters ¹		X ⁵	X ^{7,8}	X ¹⁰	
Oxygenation Measurements ²			X ⁷	X ¹⁰	
Ventilator Parameters ³			X ⁷	X ¹⁰	
AE Monitoring ⁴		X			X
Concomitant Medications	X	X			X

¹ Hemodynamic parameters include, but not limited to, Cardiac Index (CI), Cardiac Output (CO), Central Venous Pressure (CVP), Diastolic Pulmonary Arterial Pressure (dPAP), Diastolic Systemic Arterial Pressure (dSAP), Heart Rate (HR), Mean Pulmonary Arterial Pressure (mPAP), Mean Systemic Arterial Pressure(mSAP), Pulmonary Capillary Wedge Pressure (PCWP), Pulmonary Vascular Resistance (PVR), Rhythm, Systolic Pulmonary Arterial Pressure (sPAP), and Systolic Systemic Arterial Pressure (sSAP)

² Oxygenation measurements include SaO₂ or SpO₂ and PaO₂

³ Ventilator parameters include Ventilator Type, Ventilator Mode, FiO₂, Inspiratory Time, Mean Airway Pressure, Peak Inspiratory Pressure, Positive End Expiratory Pressure, and Respiratory Rate

⁴ To include unanticipated medical events in the judgment of the investigator

⁵ Measure hemodynamic parameters prior to cardiac surgery with CPB and prior to dosing with aerosolized Veletri

⁶ Initiate aerosolized Veletri dose at 50 ng/kg/min in accordance with each site's standard of care guidelines and stabilize the patient on aerosolized Veletri for at least 15 minutes

⁷ Measure hemodynamic, oxygenation, and ventilator parameters after stabilization of aerosolized Veletri

⁸ Determination of hemodynamic response from baseline for study inclusion, study continuation, and transition to VentaProst

⁹ Initiate VentaProst dose at the calculated equivalent dose of 17 ng/kg/min; titrate up in 20% increments every 15 minutes (refer to VentaProst Pharmacy Manual); continue until dose is achieved that matches the hemodynamic measurements obtained with aerosolized Veletri dosing; stabilize patient on VentaProst for at least 15 minutes

¹⁰ Measure hemodynamic, oxygenation, and ventilator parameters before and at 15 to 30 minutes after each VentaProst dose (during dosing, stabilization, and weaning [if still intubated]) and at 15 to 30 minutes after discontinuation of VentaProst

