3.2 Secondary Objectives

The secondary objectives are:

- To evaluate the safety and tolerability of VentaProst doses in a patient population post cardiac surgery with cardiopulmonary bypass (CPB)
- To demonstrate that VentaProst dose titration to achieve at least a 15% improvement in one or more hemodynamic parameters (as defined by the clinical team) is safe and effective
- To demonstrate the PD equivalence (based on cardiovascular parameters, indices of oxygenation, and ventilator support) of VentaProst doses to aerosolized Veletri doses
- To identify cardiovascular medications administered concomitantly with VentaProst
- To monitor ventilator support needed

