Once a VentaProst dose equivalence has been achieved, patients will be weaned from VentaProst. VentaProst weaning will occur from mechanical ventilation only. If the patient has been extubated and is on institution's standard of care delivery system for administering aerosolized Veletri, weaning will occur in accordance with each site's standard of care guidelines for weaning of aerosolized Veletri. The table below shows the typical weaning steps for aerosolized Veletri from mechanical ventilation. If weaning from VentaProst occurs while on mechanical ventilation, doses will be decreased in 20% increments of the VentaProst equivalent dose.

Weaning Guideline

Aerosolized Veletri (from Ventilator)	VentaProst (from Ventilator)
50 ng/kg/min	Dose Equivalence to aerosolized Veletri 50 ng/kg/min
40 ng/kg/min	80% of Dose Equivalence
30 ng/kg/min	60% of Dose Equivalence
20 ng/kg/min	40% of Dose Equivalence
10 ng/kg/min	20% of Dose Equivalence

Patients on mechanical ventilation will be weaned from VentaProst slowly due to concern that VentaProst is providing significant clinical benefit and to avoid a rebound effect. Doses will be decreased in increments of 20% of the VentaProst equivalent dose, with a minimum of 30 minutes between changes, down to 20% of the dose before discontinuation. The VentaProst weaning process should occur in isolation to other

treatment changes (no changes in inotropes, pressors or vasodilators). Patients will be observed closely before, during, and after dosing changes. In the event patients demonstrate signs of hemodynamic instability (changes in combined hemodynamic parameters) or a decrease in oxygenation indicated by either arterial or central blood oxygenation saturation during downward titration, the VentaProst dose will be returned to its previous level. Once patients have been stable for at least 15 minutes, repeat attempts at dose reduction may be undertaken. The process will continue until patients are fully weaned from VentaProst. A final PD measurement will be collected 15 to 30 minutes after discontinuation of VentaProst.

Patients will be monitored for safety and PD efficacy throughout the aerosolized Veletri and VentaProst administrations.

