12.3 Analyses Sets

All patients who are enrolled in the study and who receive at least one dose of VentaProst will be included in the intent-to-treat (ITT) analyses of pharmacodynamic and safety data. All available data will be used and missing data will not be estimated or carried forward in any statistical summary or analyses.

Descriptive summary statistics include the number of patients, mean, median, percent coefficient of variation (% CV) (if required), standard deviation, and minimum and maximum values (quantitative variables) or the number of patients and percentages by category (qualitative variables). Changes will be assessed as the difference between baseline measurements and the appropriate post-dose measurements unless otherwise specified. Individual patient listings of data will also be provided to allow for review of all pharmacodynamic, safety, and tolerability parameters.

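### Oxygenation is assessed on raw PaO2 and saturation while FiO2 may change between readings; PaO2/FiO2 from same-time readings should be added

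*Combined protocol and SAP*

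**What the plan says.** The third secondary objective in section 3.2 is "To demonstrate the PD equivalence (based on cardiovascular parameters, indices of oxygenation, and ventilator support) of VentaProst doses to aerosolized Veletri doses". The document does not say what the oxygenation indices are. Sections 7.2 and 12.5.2 list two oxygenation endpoints: arterial or pulse-oximetry saturation, and "Partial Pressure of Oxygen in Arterial Blood". FiO2 appears separately, under ventilator support.

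The footnotes to Table 1 in the synopsis match this split: "Oxygenation measurements include SaO₂ or SpO₂ and PaO₂" and "Ventilator parameters include Ventilator Type, Ventilator Mode, FiO₂, Inspiratory Time, Mean Airway Pressure". Both sets are scheduled together on VentaProst: "Measure hemodynamic, oxygenation, and ventilator parameters before and at 15 to 30 minutes after each VentaProst dose".

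On analysis, section 12.3 says: "Changes will be assessed as the difference between baseline measurements and the appropriate post-dose measurements unless otherwise specified". Section 12.5.2 adds that the key secondary efficacy endpoints will be analysed in a similar way to the primary. Section 12.1 leaves the detail to a later SAP, and no separate SAP text is in the document.

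On ventilator settings, section 6.4.2 says "The device is designed for use with standard adult ventilator settings" and requires an intermittent positive pressure mode, with no condition on FiO2. The weaning text in section 4.1 asks for separation from other "treatment changes (no changes in inotropes, pressors or vasodilators", which does not name FiO2. Section 6.6.1 lists no prohibited therapy.

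**The concern.** PaO2 depends on the oxygen fraction delivered as well as on how well the lung transfers it. If FiO2 is altered between the Veletri reading and the VentaProst reading, PaO2 moves even when gas exchange has not.

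Two features of Part I leave room for this. The order is fixed, and section 4.3.1 gives each treatment period as 24 hours or more, so time since surgery always differs in the same direction. Section 2.1 itself allows that a patient's need for pulmonary vasodilation may have improved since Veletri was started. Section 4.1 also requires SaO2 to be kept at or above its Veletri level without saying at what FiO2, so a preserved saturation could reflect a higher FiO2. Listing saturation beside PaO2 does not solve the problem, because saturation depends on FiO2 too.

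At stake is the oxygenation part of the PD equivalence objective. A difference or a similarity in PaO2 between the two products would have no clear reading for any patient whose FiO2 changed.

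**Working it through.** The plan states no figure for oxygenation: no margin, expected change, SD or power. There is nothing to reproduce. The check compares the relevant sections and then illustrates the size with assumed FiO2 values.

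**Can PaO2 and FiO2 be paired?**
- Part I, VentaProst period: yes (Table 1, footnote 10; section 10.1.4).
- Part I, on stabilised Veletri: yes (Table 1, footnote 7; section 10.1.3).
- Part I, before Veletri: yes in section 10.1.3, which lists oxygenation and ventilator parameters before administration. Table 1, footnote 5, names only hemodynamic parameters at that point.
- Part II, before VentaProst and at dose changes: yes (Table 2, footnotes 5 and 7).
- Pre-surgery baseline: no. Sections 10.1.2 and 10.2.2 schedule hemodynamic parameters only. The change-from-baseline rule in section 12.3 therefore has no pre-surgery oxygenation value to use.

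**Size at constant PaO2/FiO2 (all FiO2 values assumed)**

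Raw PaO2 change = (FiO2 after / FiO2 before) x (1 + true change in PaO2/FiO2) - 1. With no true change:
- 1.0 to 0.6: 0.6/1.0 - 1 = -40%
- 0.6 to 0.4: 0.4/0.6 - 1 = -33%
- 0.5 to 0.4: 0.4/0.5 - 1 = -20%
- 0.4 to 0.5: 0.5/0.4 - 1 = +25%
- FiO2 unchanged: 0%

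With a true 30% gain and FiO2 going from 0.6 to 0.4: (0.4/0.6) x 1.30 - 1 = -13%. A real improvement shows as a fall.

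**Check under a different physiological assumption**

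Holding PaO2/FiO2 constant makes PaO2 proportional to FiO2 by construction, so the calculation was repeated holding the arterial-to-alveolar ratio constant. Alveolar PO2 = (760 - 47) x FiO2 - 40/0.8 = 713 x FiO2 - 50, with barometric pressure 760, water vapour 47, PaCO2 40 mm Hg and R 0.8 all assumed.

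| FiO2 | Alveolar PO2 (mm Hg) | Raw PaO2 change | PaO2/FiO2 change |
|---|---|---|---|
| 1.0 to 0.6 | 663.0 to 377.8 | -43% | -5% |
| 0.6 to 0.4 | 377.8 to 235.2 | -38% | -7% |
| 0.4 to 0.5 | 235.2 to 306.5 | +30% | +4% |

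The ratio removes most of the movement caused by FiO2, but not all of it.

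**If a 90%-of-effect criterion like the primary's were carried over**

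Assume PaO2 of 100 mm Hg before Veletri and 120 on Veletri, both at FiO2 0.5, then the same gas exchange on VentaProst at FiO2 0.45.
- PaO2/FiO2: 100/0.5 = 200 before Veletri and 120/0.5 = 240 on Veletri. It stays at 240 on VentaProst.
- PaO2 on VentaProst: 240 x 0.45 = 108.
- Effect retained on raw PaO2: (108 - 100)/(120 - 100) = 8/20 = 40%.
- Effect retained on PaO2/FiO2: (240 - 200)/(240 - 200) = 100%.

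A 0.05 difference in FiO2 is enough to reverse the reading in this example.

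**The case against.** The other side has several fair points.

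- The switch is immediate: VentaProst nebulization starts and Veletri flow is then stopped. Readings are taken before and 15 to 30 minutes after each VentaProst dose. FiO2 may well be unchanged across that short step, and raw PaO2 is then interpretable. This stands for comparisons close to the switch. It does not cover change from the pre-Veletri reading, or later readings.
- FiO2 is itself an endpoint, and section 12.3 promises individual listings of all PD parameters. With about 10 patients per part, a careful reader could spot a PaO2 change driven by FiO2. That stands, but separate summaries of PaO2 and FiO2 do not give the within-patient ratio.
- No test, margin or success rule is stated for oxygenation, and the primary endpoint is hemodynamic. This stands and limits the consequence.
- The rule in section 12.3 allows other specifications, the SAP is still to come, and the objective's wording is broad enough to include PaO2/FiO2. The omission is therefore not proof that the ratio will not be analysed. But nothing in the document specifies it.
- PaO2/FiO2 is not a clean measure either. It shifts by about 4% to 7% in the constant-ratio check above, and PEEP and mean airway pressure remain unadjusted. This argues for adding it alongside the existing endpoints, not substituting it for them.

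A reader might go further and infer that FiO2 differs systematically between the two products, because one always follows the other. The documents do not support that. They report no FiO2 value, change or direction. The fixed order permits drift but does not establish it.

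**Conclusion.** The point holds as a limit on interpretation. PaO2 is unadjusted, FiO2 is not held constant, and no FiO2-adjusted measure is defined for an objective that refers to oxygenation indices. When FiO2 differs between paired readings, raw PaO2 cannot separate gas exchange from ventilator setting. Under the assumed FiO2 changes of 0.1 to 0.4, PaO2 moves by about 20% to 40% in either direction with gas exchange unchanged. If FiO2 is unchanged, raw PaO2 and PaO2/FiO2 give the same percentage change.

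These sizes rest on assumed FiO2 values. The actual distortion cannot be known from the documents. It would therefore be wrong to conclude that the oxygenation comparison reflects FiO2 adjustment rather than drug effect, or that equivalence would be decided by it. The endpoint is secondary and descriptive, with about 10 patients per part, and the primary endpoint is unaffected. The change is worth making because it is cheap and the inputs are already scheduled together at the readings that matter.

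**What to change.** 1. In sections 7.2 and 12.5.2 and in the SAP, define the oxygenation indices named in section 3.2 to include PaO2/FiO2, computed from PaO2 and FiO2 recorded at the same time.
2. State the reference reading for its change: the pre-Veletri reading in Part I and the pre-VentaProst reading in Part II. The pre-surgery baseline schedules no oxygenation measurement.
3. Align Table 1, footnote 5, with section 10.1.3, so that the pre-Veletri oxygenation and ventilator readings appear in both places.
4. Keep PaO2, SaO2 or SpO2, and FiO2 as summarised endpoints beside the ratio. FiO2 also serves the separate objective of monitoring ventilator support, so it should not be reduced to a listing.
5. Settle the definition before database lock, so that the index is not chosen after the results are seen.

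The cost is one extra derived variable. Relative to section 10.1.3 and Table 2, no new measurement is needed, and ventilator management does not change. The downside is that PaO2/FiO2 still depends somewhat on FiO2 and airway pressure. Reporting FiO2 and the recorded ventilator pressures next to it lets the reader judge that.

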- Measure hemodynamic, oxygenation, and ventilator parameters before and at 15 to 30 minutes after each VentaProst dose adjustment and at 15 to 30 minutes after discontinuation of VentaProst
- Record all concomitant medications
- Record AEs

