12.5.2 Secondary Endpoints

Key secondary endpoints include:

- Safety of VentaProst dosing regimen
 - Monitoring of AEs, physical examinations, laboratory tests, and electrocardiograms
- Effect of VentaProst dosing regimen on:
 - Cardiovascular Parameters
 - Pulmonary Vascular Resistance (PVR)
 - Pulmonary Arterial Pressure (PAP)
 - Systemic Arterial Pressure
 - Central Venous Pressure (CVP)
 - Pulmonary Capillary Wedge Pressure (PCWP)
 - Cardiac Output (CO)
 - Oxygenation
 - Arterial Oxygen Saturation (SaO_2) or Oxygen Saturation by Pulse Oximetry (SpO_2)
 - Partial Pressure of Oxygen in Arterial Blood (PaO_2)
 - Ventilator Support
 - FiO_2
 - Ventilator pressures
 - Ventilator volumes
 - Duration of intubation
 - Number and type of cardiovascular medications required through end of study

Similar analyses for the primary endpoint will be applied to the key secondary efficacy endpoints.

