13.2.3 Monitoring Procedures

The Sponsor or Sponsor's representative will maintain contact with the Investigator and designated staff by telephone, letter, and/or email between study visits. Monitoring visits to each investigational site will be conducted by the assigned CRA. The Investigator will allow the CRA to inspect the clinical, laboratory, and pharmacy facilities to assure compliance with GCPs and local regulatory requirements. The CRFs and patient's corresponding original medical records (source documents) are to be fully available for review by the Sponsor's representatives at regular intervals. These reviews verify adherence to study protocol and data accuracy in accordance with federal regulations and

local regulations. All records at the investigational site are subject to inspection by the FDA.

In accordance with ICH E6, Section 6.10, source documents include, but are not limited to the following:

- Clinic, office, hospital charts.
- Copies or transcribed health care provider notes which have been certified for accuracy after production.
- Recorded data from automated instruments such as mechanical ventilators, x-rays, and other imaging reports, e.g., sonograms, computed tomography scans, magnetic resonance images, radioactive images, ECGs, rhythm strips, electroencephalographs, polysomnographs, pulmonary function tests (regardless of how these images are stored, including microfiche and photographic negatives).
- Records of telephone contacts.
- Diaries or evaluation checklists.
- Investigational product distribution and accountability logs maintained in pharmacies or by research personnel.
- Laboratory results and other laboratory test outputs, e.g., serum pregnancy test result documentation.
- Correspondence regarding a study patient's treatment between physicians or memoranda sent to the IRBs/IECs.
- CRF components (e.g., questionnaires) that are completed directly by patients and serve as their own source.

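### Ventilator volumes are a secondary endpoint, but the protocol specifies no volume for collection, so the endpoint cannot be reported from the data the protocol requires

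*Combined protocol and SAP*

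**What the plan says.** Section 7.2 lists "Ventilator volumes" among four ventilator-support measures; the other three are FiO2, ventilator pressures and duration of intubation. The synopsis has the same list. So does section 12.5.2, which calls these endpoints key and adds: "Similar analyses for the primary endpoint will be applied to the key secondary efficacy endpoints".

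What is to be recorded is set out in the two schedules. Footnote 3 is the same in Table 1 (Part I) and Table 2 (Part II): "Ventilator parameters include Ventilator Type, Ventilator Mode, FiO₂, Inspiratory Time, Mean Airway Pressure, Peak Inspiratory Pressure, Positive End Expiratory Pressure, and Respiratory Rate".

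Footnote 1 of the same tables is worded differently. It opens "Hemodynamic parameters include, but not limited to, Cardiac Index (CI" and so marks its list as open. Footnote 3 has no such phrase.

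The visit text relies on the general term. Section 10.1.4.2, for example, says: "Measure hemodynamic, oxygenation, and ventilator parameters before and at 15 to 30 minutes after each VentaProst dose adjustment".

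**The concern.** An endpoint needs a matching item in the list of data to be collected. Here the endpoint is stated three times, and the list that should feed it contains no volume in either part. A site that recorded exactly what footnote 3 names would have nothing to report under this heading.

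The gap could not be closed at the analysis stage. Section 12.3 says that "missing data will not be estimated or carried forward in any statistical summary or analyses". Section 12.1 leaves the detailed methods to an analysis plan to be finalized before database lock, but such a plan can only use readings that someone took at the bedside.

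Ventilator support is also one of the three bases named for the secondary objective of PD equivalence (section 3.2), so one component of that comparison would be missing.

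**Working it through.** No figure in the plan is at issue, so the check is a match between the endpoint list and the collection list.

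**Step 1. Match each ventilator-support endpoint to footnote 3 (eight items, the same in Parts I and II).**

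| Endpoint (synopsis, 7.2, 12.5.2) | Matching items in footnote 3 |
|---|---|
| FiO2 | 1 (FiO2) |
| Ventilator pressures | 3 (mean airway, peak inspiratory, positive end-expiratory) |
| Ventilator volumes | 0 |
| Duration of intubation | 0 (an elapsed time, not a ventilator reading) |

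The other four of the eight items are ventilator type, mode, inspiratory time and respiratory rate.

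**Step 2. Look for a volume elsewhere.** Sections 10.1.3, 10.1.4.1 and 10.1.4.2 (Part I), sections 10.2.3.1 and 10.2.3.2 (Part II), and sections 4.2 and 4.6 call for ventilator parameters or ventilator support without naming a volume. No tidal, minute or other ventilator volume appears as a measurement anywhere. The word otherwise occurs for volume of distribution and stroke volume (section 2.1) and for droplet size (section 6.4.1.1).

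**Step 3. Ask whether a volume can be derived.**

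- Tidal volume = mean inspiratory flow × inspiratory time. Time is listed; flow is not.
- Tidal volume = compliance × pressure change. Pressures are listed; compliance is not.
- Minute ventilation = tidal volume × respiratory rate. Rate is listed; tidal volume is not.

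Each route lacks a term. The delivery system does contain a flow sensor (section 6.4.1.1), but its stated use is to time the aerosol to the breath. Nothing asks for its output to be recorded.

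**Step 4. Size.** About 10 patients are planned in each part, so 10 + 10 = about 20. If the eCRF carries only the footnote 3 items, 0 of about 20 would have a volume, and 1 of the 4 ventilator-support measures would be empty. If the eCRF has a volume field, or sites record volumes unprompted, the loss is smaller and may be nil.

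**The case against.** The strongest reply is that the schedule footnotes are not complete inventories. Footnote 3 uses the verb include, which need not be exhaustive. Duration of intubation is another ventilator-support endpoint missing from it. Central venous oxygenation is considered during titration (section 4.2) but is absent from footnote 2. Section 7.2 says the listed endpoints are to be assessed, which is itself some direction to sites. Section 13.2.3 names as source documents "Recorded data from automated instruments such as mechanical ventilators", so volumes might be retrieved later. The eCRF and its completion guidelines were not available to check.

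Much of this stands, and it limits the conclusion. A reader might infer that volumes will never be collected, or that the endpoint will certainly have no data. The documents do not support that: it would require footnote 3 to be closed and the eCRF to copy it, and neither is shown. A reader might also infer that volumes are needed to interpret aerosol delivery, because the device works only during inspiration (section 2.2.6). No section makes that link. Section 6.4.1.1 sets the dose by pump rate and ideal body weight, so the argument should not be used.

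What the reply does not do is point to any requirement to record a volume. Even if footnote 3 is read as open, it leaves open whether a volume is taken, which one and when, at approximately three sites. The source-document clause concerns verification and asks nobody to extract a volume. Duration of intubation is a weaker parallel, since it is an elapsed time that can ordinarily be taken from the chart afterwards.

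**Conclusion.** The point holds as an inconsistency between the endpoint list and the collection schedule, in both parts of the study. The protocol names ventilator volumes as a secondary endpoint three times and specifies no volume for collection, and none can be derived from what is listed. The endpoint cannot be reported from the data the protocol requires.

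The figure of 0 of about 20 patients is conditional on the eCRF mirroring footnote 3, and should be quoted only with that condition.

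The consequence is small. One descriptive secondary measure is affected. The primary endpoint is a dose defined by hemodynamic response and does not use volumes. The sample size rationale in section 12.2 does not depend on them, and they are not named in the titration, weaning or conversion criteria. The correction is still worth making, because an unrecorded bedside reading may not be recoverable later and the remedy is cheap.

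**What to change.** Check the eCRF first. If it already has a volume field, only footnote 3 needs to be brought into line. Otherwise choose one of two courses:

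1. Keep the endpoint. State which volume is meant, with units (tidal volume and minute ventilation are examples; the documents do not say which was intended). Add it to footnote 3 of Tables 1 and 2 and to the eCRF, to be recorded at the ventilator readings already scheduled.
2. Drop the endpoint. Delete ventilator volumes from the synopsis, section 7.2 and section 12.5.2.

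The first course costs one or two extra eCRF fields and adds no new time points. The second costs a text change in three places.
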